This study will adapt and integrate a novel PrEP initiation intervention at point of care in rural SSPs using strengths-based case management (SBCM) approaches to elicit and address structural, environmental and psychosocial barriers to PrEP care. Participants will be randomized into: CDC-PrEP (an in-use PrEP intervention based on CDC guidelines), or the experimental SBCM-PrEP intervention. CDC-PrEP utilizes structured risk assessments and educational materials recommended by the CDC and operates as a point of care model with embedded APRNs providing clinical screening, prescribing, and monitoring of patients in a single session. SBCM-PrEP provides up to 5 strengths-based sessions to deliver tailored PrEP education and engage in action planning to increase readiness for PrEP initiation.

The rationale for the selection of the intervention comparators is threefold:

- 1) use of an active comparator (CDC-PrEP) meets an ethical standard to provide high-risk participants with needed basic education and the potential to access PrEP;
- 2) examination of a brief, in-use content specific intervention for PrEP based on CDC guidelines affords the opportunity to establish preliminary efficacy of an existing intervention that has not been formally tested within the SSP context, and whose brevity may contribute to scalability if efficacious; and
- 3) Comparison with the SBCM-PrEP will examine the value-added of a more robust, but brief, client-driven intervention that supports PrEP initiation through active advocacy to reduce multi-level barriers to uptake.

Objectives	7	Specific objectives or hypotheses
		
The primary objective is to examine preliminary efficacy and effect sizes of the novel SBCM-PrEP and CDC-PrEP interventions on the primary outcome of PrEP initiation (measured by dispensed PrEP prescription) in HIV- participants who inject drugs.

Trial design	8	
Description of trial design including type of trial (eg, parallel group, crossover, factorial, single group), allocation ratio, and framework (eg, superiority, equivalence, noninferiority, exploratory)
 
The trial is designed as a randomized, controlled exploratory trial with two parallel groups and a primary endpoint of PrEP initiation during 3 months after enrollment. Randomization will be stratified by site and gender and performed with a 1:1 allocation.

Methods: Participants, interventions, and outcomes

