Sample size 14 Estimated number of participants needed to achieve study objectives and how it was determined, including clinical and statistical assumptions supporting any sample size calculations

The pilot RCT is not designed to establish superiority of the SBCM-PREP, but to generate valid parameter estimates and preliminary evidence of effect sizes for application in a subsequent large trial. The proposed sample size of 80 aligns with recommended sample sizes for two-arm pilot trials structured as planning for subsequent major trials. Assuming a retention rate of 90% at 6 months, there will be 36 participants per intervention group for analysis, which is sufficient.

Recruitment 15 Strategies for achieving adequate participant enrolment to reach target sample size

Recruitment is balanced across the two SSP locations and by gender, targeting enrollment of 40 individuals per location, or 80 in total. Within the SSP settings, potential participants will be screened by research staff on rotating days of the week when the SSPs are operational and eligible participants will be invited to participate. Approximately 6-8 individuals will be enrolled into the study each month across the two sites; challenges meeting the enrollment target based on prior research in these settings and current volumes of SSP clients are not anticipated.

Methods: Assignment of interventions (for controlled trials)

Allocation:

Sequence generation 16a Method of generating the allocation sequence (eg, computer-generated random numbers), and list of any factors for stratification. To reduce predictability of a random sequence, details of any planned restriction (eg, blocking) should be provided in a separate document that is unavailable to those who enroll participants or assign

interventions

Participants will be randomly assigned to either the CDC-PrEP or SBCM-PrEP with a 1:1 allocation per a computer-generated randomization schedule stratified by site and gender.

Allocation concealment mechanism	16b	Mechanism of implementing the allocation sequence (eg, central telephone; sequentially numbered, opaque, sealed envelopes), describing any steps to conceal the sequence until interventions are assigned -The study coordinator and PI are notified of the allocation via secure email.

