Study instrumentation will collect self-report information on participation in PrEP screening, prescription, and adherence, however, primary measures will be drawn from HD/SSP medical record data to be extracted from the Patient Encounter Form (PEF) and Adult History and Physical Form through chart review at 3-and 6-months post baseline. Data points planned for extraction include: visit date, visit location (including phone or telehealth), provider number, patient ID number, CPT visit type, ICD codes, current medications, laboratory tests conducted relevant to CDC PrEP guidelines (HIV testing, viral hepatitis testing, STI testing, kidney function, and pregnancy testing), and PrEP prescription issuance/refills. For participants who receive a PrEP prescription from the nurse-interventionist, provider-initiated pharmacy verification and/or participant prescription documentation will be used to verify that the prescription was dispensed to the patient.

Well-validated measures will examine participant and risk environment characteristics that may influence intervention outcomes. These measures will be collected at baseline, 3-and 6- month follow-up. The primary data collection instrument contains abbreviated segments of: a. Global Appraisal of Individual Needs (GAIN, v. 5.4) to capture demographics, substance use, physical and mental health, violence, housing situation, transportation; b. Collaborative Injection Drug User Study III/Drug User Intervention Trial Assessment Instrument to capture injection behaviors and equipment sharing, and sources of injecting equipment including SSPs; c. items on secondary syringe exchange, syringe disposal, and syringe coverage, d. Community Stigma related to substance use; and, e. Law Enforcement Activity near or enroute to SSP locations. Validated measures of perceived HIV risk, HIV-related community stigma, PrEP awareness, acceptability, and use, dignity denial, and PrEP adherence at follow-up have been included.

18b Plans to promote participant retention and complete follow-up, including list of any outcome data to be collected for participants who discontinue or deviate from intervention protocols

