Statistical methods	
20a Statistical methods for analysing primary and secondary outcomes. Reference to where other details of the statistical analysis plan can be found, if not in the protocol
 
A total of 80 HIV- rural PWID will be randomly assigned to the two intervention groups. The major interest in Specific Aim 3 is to evaluate the preliminary efficacy of the intervention conditions on PrEP initiation (measured by dispensed PrEP prescription) at 3- and 6-month follow-ups. With 36 participants per intervention condition, and utilizing a 95% confidence interval, we will be able to estimate the true probability of PrEP initiation for either trial arm within a maximum of ± 0.16. To address Aim 3, robust analytic methods will be used for descriptive purposes and data analyses. Descriptive statistics (e.g., frequencies, proportions, means, and standard deviations) will be used to describe process variables (e.g., the number of sessions attended, engagement scores). Bivariable analyses will be used to examine potential differences in feasibility and acceptability between the two study conditions. Conventional statistical methods, such as t-tests, Chi- square, ANOVA, ANCOVA, OLS, and logistic regression will be used for preliminary analyses of the demographic and risk environment characteristics of PWID, as well as those associated with PrEP initiation. Tests will be two-sided at the 0.05 level. Similarly, to examine initiation of PrEP, as well as continuation of PrEP among those who initiated by 3 months, we will utilize frequencies, proportions, and corresponding 95% confidence intervals. Additionally, logistic regression models will be utilized to assess for group differences, adjusting for site due to its use as a stratification factor.
 
20b Methods for any additional analyses (eg, subgroup and adjusted analyses)
 
N/A
 
20c Definition of analysis population relating to protocol non-adherence (eg, as randomised analysis), and any statistical methods to handle

---------------------	---

missing data (eg, multiple imputation)

We will use an intent-to-treat approach, analyzing data from all participants based on the trial arms to which they were randomized regardless of whether they receive or complete the randomized treatment to which they were assigned.

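### The between-arm model adjusts for site only; pre-specifying one baseline score already being collected would modestly protect and sharpen the pilot's risk-difference estimate

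*Combined protocol and SAP*

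**What the plan says.** Item 20a and the analysis text under the SAP's Statistical Design and Power heading describe one between-arm model: "logistic regression models will be utilized to assess for group differences, adjusting for site due to its use as a stratification factor". Item 20b, the place for adjusted analyses, is marked N/A.

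Item 18a describes the covariate data: "Well-validated measures will examine participant and risk environment characteristics that may influence intervention outcomes". It says these are collected at baseline, 3 and 6 months. The closing sentence of that item adds "Validated measures of perceived HIV risk, HIV-related community stigma, PrEP awareness, acceptability, and use", among other scales.

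Regression on characteristics associated with initiation does appear in item 20a, but as preliminary analysis. Nothing says that any of these characteristics enters the arm comparison.

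On design, item 8 states: "Randomization will be stratified by site and gender and performed with a 1:1 allocation". Item 14 and the SAP say that the pilot is meant to supply parameter estimates and effect sizes for a larger trial, not to show superiority.

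**The concern.** The plan identifies characteristics that may drive the outcome, measures them before treatment, and then leaves them out of the one comparison the pilot exists to deliver. Stratifying by site and gender does not balance readiness to use PrEP. With 40 per arm, a chance difference in such a score moves the observed risk difference, and the site-only model cannot correct for it. Because estimation is the stated purpose, the fact that superiority is not the aim does not remove the interest in a sharper estimate. What is at stake is the quality of one effect size passed to the next trial, not the validity of a test.

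**Working it through.** **Inputs from the documents.** Item 20a: "A total of 80 HIV- rural PWID will be randomly assigned to the two intervention groups", so 40 per arm at 1:1. Item 14: "Assuming a retention rate of 90% at 6 months, there will be 36 participants per intervention group for analysis". Item 20a: "Tests will be two-sided at the 0.05 level". Item 20c says that the primary outcome comes from records and should be unaffected by dropout, so 40 per arm is used below.

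**The plan's own figure.** The plan expects to "estimate the true probability of PrEP initiation for either trial arm within a maximum of ± 0.16". With 80 × 0.90 / 2 = 36 per arm, 1.96 × √(0.25/36) = 0.163, so the figure reproduces. The worst-case half-width for the difference between arms is 1.96 × √(0.5/36) = 0.23, or 1.96 × √(0.5/40) = 0.22 with all 80.

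**Size of chance imbalance.** The standardised difference between arms on any one baseline score has SD √(2/40) = 0.224. The median absolute imbalance is 0.6745 × 0.224 = 0.15 SD. It exceeds 0.25 SD in 26% of randomisations and 0.5 SD in 2.5%.

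**Assumptions.** The documents give no initiation rates and no association with any score. Assumed: CDC-PrEP v SBCM-PrEP rates of 10% v 25%, 25% v 45%, 30% v 60% and 30% v 30%; a standard normal score; odds ratio (OR) per SD of the score from 1 to 3; arms balanced within site.

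**Simulation.** 4,000 trials per scenario compared logistic regression on arm + site with arm + site + score. The risk difference was standardised over the sample. Two of the four rate pairs:

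| Rates | OR per SD | SD of risk difference: site only → with score | Variance change | SE of log OR: site only → with score |
|---|---|---|---|---|
| 10% v 25% | 1 | 0.0843 → 0.0849 | +1.5% | 0.655 → 0.665 |
| 10% v 25% | 1.5 | 0.0816 → 0.0815 | −0.2% | 0.652 → 0.677 |
| 10% v 25% | 2 | 0.0829 → 0.0810 | −4.4% | 0.655 → 0.699 |
| 10% v 25% | 3 | 0.0821 → 0.0770 | −12.2% | 0.652 → 0.739 |
| 25% v 45% | 1 | 0.1046 → 0.1052 | +1.2% | 0.493 → 0.499 |
| 25% v 45% | 1.5 | 0.1062 → 0.1053 | −1.7% | 0.492 → 0.510 |
| 25% v 45% | 2 | 0.1041 → 0.1002 | −7.4% | 0.492 → 0.529 |
| 25% v 45% | 3 | 0.1050 → 0.0950 | −18.2% | 0.493 → 0.568 |

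The other two pairs gave variance changes of +1.0% to +1.3% (OR 1), −1.6% to −2.1% (1.5), −5.8% to −7.7% (2) and −15.7% to −16.4% (3). Further runs, including a linear model with HC3 standard errors, widen the ranges to falls of 0-3%, 3-9% and 10-18%, and a rise of about 1-2% for an unrelated score. The linear model's adjusted coverage was 95-96%, including at 10% v 25%.

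**On the CI scale.** At 25% v 45% the half-width goes from 1.96 × 0.1041 = 20.4 to 1.96 × 0.1002 = 19.6 points at OR 2, and from 20.6 to 18.6 points at OR 3.

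**Shift from one imbalance.** The site-only risk difference moves by 0.053-0.085 per SD of imbalance (OR 1.5), 0.086-0.140 (OR 2) or 0.131-0.200 (OR 3).
- Times 0.224, this is about 1.2-1.9, 1.9-3.1 and 2.9-4.5 points.
- At the 95% limit, 1.96 × 0.224 = 0.44 SD, it is about 2-4, 4-6 and 6-9 points.
- With the score in the model, the shift at that limit is about 1 point or less.

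**Validity.** Averaged over randomisations, both models give the same mean risk difference to within 0.001. At 30% v 30% the rejection rate was 4.5-5.1% for site only and 4.3-5.5% with the score.

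**Sparse outcomes.** At 10% v 25% there are 40 × 0.10 + 40 × 0.25 = 14 expected initiators. Between 1% and 2% of fits failed there, in equal numbers for the two models.

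**The case against.** The strongest reply is that nothing here is invalid. Chance imbalance is ordinary sampling error and the 95% CI already allows for it. That stands. A reader might infer that the site-only model is biased, or that it wrongly credits an imbalance to one intervention; the plan's randomised design and the results above do not support this.

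A reader might also infer that the planned logistic regression loses precision by omitting the score. On its own scale it does not: the SE of the log odds ratio rises on adjustment in every scenario. Part of the reason is that the adjusted odds ratio is a different, conditional quantity. The gain appears on the standardised risk difference, which the plan does not mention.

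Third, the choice of PrEP acceptability is a judgement. Item 18a gives it no strength of association, instrument or score range. Baseline collection is the natural reading, but the sentence naming acceptability follows the timing statement and also includes a follow-up-only scale (adherence). Other measures, such as perceived HIV risk, stigma or transportation, could be argued for. This stands too, so acceptability is offered only as an example.

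Fourth, learning which characteristics predict initiation is a reasonable pilot task in itself. It is, but it does not stop the plan from naming one covariate in advance.

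**Conclusion.** The concern holds in a limited form. The arm comparison uses site alone although the trial plans to hold baseline information that it says may matter, and item 20b offers no adjusted analysis. The site-only analysis remains valid and unbiased.

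The gain depends on an association that the documents do not give. It is negligible at an odds ratio of 1.5 per SD, small at 2 and worthwhile at 3. In sample-size terms, a 7.4% fall in variance is worth 80/0.926 ≈ 86 participants instead of 80, and an 18.2% fall is worth 80/0.818 ≈ 98. Power rises 5-7 points at an odds ratio of 3, but power is not a design target here and should not carry the argument. The case for change is that one unblinded, 80-person estimate will feed the next trial and that the cost of protecting it is very low. The figures assume a continuous, roughly normal score and arms balanced within site.

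**What to change.** In item 20a and the SAP, before any outcome data are seen:

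- Name one baseline score, for example PrEP acceptability, after confirming that it is collected at baseline and scored as a continuous measure. Use the baseline value only.
- Fit the arm model with that score and both stratification factors. Site is included because randomisation was stratified on it, and the same reasoning applies to gender.
- Report the standardised risk difference with its 95% CI, alongside the site-only estimate.
- Choose one estimation method in advance: the logistic model with standardisation, or the linear model with HC3 standard errors (item 20a already lists OLS and ANCOVA). If a switch is wanted when initiators are few, state the number that triggers it, so that the model cannot be chosen after the results are seen.
- Replace the N/A at item 20b with a reference to this analysis.

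The cost is a few sentences and no new data. The score adds one parameter (about 1-2% more variance if it proves unrelated to initiation). Any odds ratio from the adjusted model is conditional on the score and should be labelled so.

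### Randomisation is stratified by site and gender, but the between-arm logistic model adjusts for site only, for a reason that applies equally to gender

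*Combined protocol and SAP*

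**What the plan says.** Item 8 (Trial design): "Randomization will be stratified by site and gender and performed with a 1:1 allocation". Item 16a (Sequence generation) repeats it: participants are assigned "with a 1:1 allocation per a computer-generated randomization schedule stratified by site and gender". Item 15 (Recruitment) also balances enrolment on both factors: "Recruitment is balanced across the two SSP locations and by gender, targeting enrollment of 40 individuals per location, or 80 in total".

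For the comparison of arms, item 20a (Statistical methods) specifies logistic regression, "adjusting for site due to its use as a stratification factor". The Aim 3 analytic plan in the statistical design section uses the same sentence. Both set tests two-sided at 0.05. Item 20b, on additional and adjusted analyses, is marked not applicable.

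On purpose, item 14 (Sample size) says the pilot is meant to "generate valid parameter estimates and preliminary evidence of effect sizes for application in a subsequent large trial".

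**The concern.** The plan states a rule, that a factor used to stratify randomisation goes into the model, and applies it to one of its two factors. Nothing in the documents separates gender from site in this respect.

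Two things follow if gender predicts PrEP initiation:

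- Stratified allocation that balances gender between arms removes the gender contribution to the variability of the arm difference. A model without gender does not know this and reports a standard error that is too large. Its confidence interval is then too wide and its test conservative.
- The odds ratio is non-collapsible. The site-only odds ratio is not biased, but it is a different and smaller quantity than the odds ratio conditional on both stratification factors. A pilot whose product is an effect size for a later trial should say which of the two it reports.

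**Working it through.** **Inputs from the documents.** N = 80, two sites with 40 each, recruitment balanced by gender, 1:1 allocation, two-sided 0.05. The documents give no initiation rates, no arm effect and no gender effect.

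**The plan's own figure.** Analysable n per arm = 80 × 0.90 / 2 = 36. Maximum half-width = 1.96 × √(0.25/36) = 0.163, which agrees with the stated ±0.16. It is a single-arm figure, does not depend on the model, and is unaffected by this point.

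**Assumptions.** Twenty participants in each of four site-by-gender cells, split 10:10 between arms; no site effect; control-arm initiation rates by gender as listed below; conditional arm odds ratio of 1 or 3.

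**Which odds ratio the site-only model targets.** Take 50/15% with conditional odds ratio 3.

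- Control mean: (0.50 + 0.15)/2 = 0.325, odds 0.325/0.675 = 0.4815.
- Experimental arm: odds 1 × 3 = 3 gives 0.75; odds (0.15/0.85) × 3 = 0.529 gives 0.346; mean 0.548, odds 1.213.
- Odds ratio averaged over gender: 1.213/0.4815 = 2.52.

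The same steps give 2.86 (50/30), 2.82 (40/20), 2.54 (40/10) and 2.29 (70/20).

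**Why the site-only test is conservative under balance.** Under the null, the site-only model uses the variance p(1 − p) at the mean rate, while the variability that remains after balancing is the mean within-gender variance.

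- 50/15%: 0.325 × 0.675 = 0.2194 against (0.25 + 0.1275)/2 = 0.1888. The standard error is overstated by √(0.2194/0.1888) = 1.08 in large samples. The effective critical value is 1.96 × 1.08 = 2.11, a type I error of about 3.5%.
- 70/20%: 0.45 × 0.55 = 0.2475 against (0.21 + 0.16)/2 = 0.185. Ratio 1.16, critical value 2.27, type I error about 2.3%.
- 50/30%: 0.24 against 0.23. Ratio 1.02, type I error about 4.5%.

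**Simulation at N = 80** (20,000 trials per scenario, logistic Wald test; each pair is site-only / site + gender):

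| Control initiation by gender | Implied gender OR | Type I error, % | Power at OR 3, % | Median OR (true conditional OR 3) |
|---|---|---|---|---|
| 50/30 | 2.3 | 4.7 / 5.1 | 66.0 / 66.2 | 2.91 / 3.16 |
| 40/20 | 2.7 | 4.2 / 4.9 | 63.6 / 64.4 | 2.89 / 3.17 |
| 50/15 | 5.7 | 3.3 / 4.9 | 54.2 / 59.1 | 2.55 / 3.17 |
| 40/10 | 6.0 | 3.6 / 5.0 | 49.1 / 56.4 | 2.58 / 3.17 |
| 70/20 | 9.3 | 2.9 / 4.95 | 45.4 / 54.3 | 2.30 / 3.15 |

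The site-only median standard error against the actual standard deviation under the null is 0.484 against 0.464 at 50/15 (4% too large) and 0.455 against 0.403 at 70/20 (13% too large). These excesses are a little smaller than the large-sample ratios.

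**Without balance within strata.** The documents do not describe blocking. With simple 1:1 allocation, the site-only type I error is 4.7 to 5.3%, so the conservatism disappears. The power gap remains: 51.0 against 57.6% at 50/15, and 43.8 against 52.8% at 70/20.

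**Separate check with other assumptions.** With mean control initiation of 20% or 40% and gender odds ratios of 1 to 8, there is almost no difference at gender odds ratios of 1 to 2. At 4 to 8, site-only loses about 2 to 8 points of power, and its type I error falls as low as 2.5%.

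**The case against.** The textual mismatch is not in dispute; its importance is. The strongest points are these.

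- **The harm needs a strong gender effect that nothing in the documents supports.** The loss of 5 to 9 points requires gender odds ratios of about 5.7 to 9.3. At 2.3 it is 0.2 points and at 2.7 it is 0.8 points. This stands.
- **The trial is an exploratory pilot, not designed to show superiority, with no power target.** Its sizing rests on per-arm precision, and the per-arm proportions with their intervals are reported in any case and could be used to plan the next trial. This stands and limits the consequence. The plan nevertheless specifies a between-arm model and tests at 0.05.
- **The conservatism depends on balanced allocation.** This stands too. The power gap does not depend on it.
- **With few events, a smaller model is defensible.** At assumed rates of 20/10%, power is 48.4 against 49.7%. At 15/5% it is 34.0 against 36.9%, and under the null the share of separated fits rises from 4.9% to 16.2%, mostly in the gender term. This could be a good reason to omit gender, but the plan does not give it.
- **Gender will be examined as a characteristic associated with initiation.** That is planned, but it does not put gender into the comparison of arms.

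**Conclusion.** The concern holds. The plan stratifies by two factors, adjusts for one, and gives a reason that covers both. The inconsistency itself rests on the text alone and needs no assumption.

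The practical effect ranges from negligible, if gender is weakly related to initiation, to moderate, if the relation is strong. The moderate end is a conservative test under balanced allocation, about 5 to 9 points of power, and a reported odds ratio of about 2.3 to 2.5 where the one conditional on both factors is 3. Those figures assume the initiation rates shown and a conditional odds ratio of 3. The omission causes no inflation of false positives and no bias in the site-only odds ratio as an estimate of its own target. It is worth correcting because the correction is cheap and because settling the model in advance avoids a choice between two odds ratios once results are known, in a trial that is not blinded.

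**What to change.** In item 20a and in the Aim 3 analytic plan, name both site and gender as covariates in the between-arm logistic model, as the two stratification factors. Alternatively, keep site alone and state why gender is left out. In either case, say which factors the reported odds ratio is conditional on.

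A fallback for few events would be useful, though the correction does not depend on it: Firth penalised logistic regression, or a Mantel-Haenszel analysis stratified by site and gender.

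The cost is a few words in two places. Gender is already collected for randomisation. Statistically, it adds one parameter. The ordinary site-and-gender fit overstates slightly in small samples (median odds ratio about 3.16 for a true 3), and cells may be sparse if initiations are few. Firth brings the median to 2.91 to 2.97, but its Wald test is somewhat conservative (type I error 3.8 to 4.2%), so it is better kept as a fallback than made the main analysis.
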